10 MEASUREMENTS

Primary Outcome Measure: Response rate according to RECIST v1.1 at 6 weeks

- RECIST v1.1 response rate, specifically, the sum of CR and PR per RECIST v1.1
- **Time Frame:** 6 weeks
- **Safety Issue:** Not a safety issue primary endpoint

10.1 Primary and Secondary Outcome measures

The primary endpoint will be tumor response rate (CR + PR) at 6 weeks. We intend to use modified RECIST v1.1 criteria {Eisenhauer, 2009}, knowing that since this patient population will include presurgical subjects, we will be unable to obtain response confirmation following the surgical resection of tumors. {Eisenhauer, 2009 #311}

10.1.1 Measurement Definition

The definition we will use for the primary endpoint of response will be per the RECIST v1.1 criteria, with the exception that for patients undergoing surgical resection there will be no confirmatory imaging as this would be irrelevant following surgical resection. CR, PR, SD, PR are all defined in the cited RECIST reference and are widely available and therefore will not be repeated here.

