1.0 OBJECTIVES

1.1 Primary Objectives

To observe the response rate of ameloblastoma to dabrafenib plus trametinib at 6 weeks.

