2.2 Study Agents

Dabrafenib is a kinase inhibitor indicated for the treatment of patients with unresectable or metastatic melanoma with BRAF-V600E mutation as detected by an FDA-approved test. Dabrafenib is an inhibitor of some mutated forms of BRAF kinases with in vitro IC50 values of 0.65, 0.5, and 1.84 nM for BRAF-V600E, BRAF-V600K, and BRAF-V600D enzymes, respectively. It is manufactured in 50 and 75 mg capsules.

According to the FDA approved package insert, the safety of dabrafenib has been evaluated in 586 patients with BRAF-mutant melanoma, including 181 patients treated for at least 6 months and 86 additional patients for 12 months. The most commonly occurring adverse reactions in these patients treated with dabrafenib were, in order of decreasing frequency hyperkeratosis, headache, pyrexia, arthralgia, papilloma, alopecia, and palmar-plantar erythrodysesthesia syndrome (PPES). The most frequent adverse reactions leading to dose reduction of dabrafenib were pyrexia (9%); PPES (3%); chills (3%); fatigue (2%); and headache (2%).

Dabrafenib has been demonstrated to induce response rates of 52% with a duration median of 5.6 months, in patients with BRAF-mutant melanoma. There are presently no safety or efficacy data for dabrafenib in patients with BRAF-mutant ameloblastoma. Dabrafenib is not FDA approved for treatment of patients with ameloblastoma, therefore conduct of this study will be under either an IND or FDA authorized IND exemption.

Trametinib is a kinase inhibitor of MEK1 and MEK2 FDA-approved for use in patients with metastatic V600E mutated melanoma based upon a randomized control trial (RCT) of trametinib vs chemotherapy in which PFS (4.8 vs 1.5 mo) and RR (22% vs 8%) were

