10.1.3 Measurement Time Points

Initial response evaluation for the primary endpoint will be at 6 weeks. For patients not undergoing surgical resection, follow-up imaging will be every 6 to 9 weeks, which we consider to be standard of care.

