12 STATISTICAL CONSIDERATIONS

12.1 Statistical Design and primary analysis

We propose a two stage Optimal design per Simon, *et al.* (Simon R, 1989. *Controlled Clinical Trials*. 10:1-10), and using the UNC calculator:

<http://www.csc.unc.edu/csc/aivanova/SimonsTwoStageDesign.aspx>

The null hypothesis that the true response rate is 0.05 will be tested against a one-sided alternative. In the first stage, 9 evaluable patients will be accrued. If there is less than one response (defined in Section 10.1) in these 9 patients, the study will be stopped. If at the time of the 9th patient's enrollment there has not been at least one centrally documented response, accrual will stop until responses have been centrally determined for the first nine patients. Otherwise, 8 additional evaluable patients will be accrued for a total of

17 evaluable patients. The null hypothesis will be rejected if 3 or more responses are observed in 17 patients. We will allow for up to 11 patients in the first stage and up to 10 patients in the second stage to account for patient drop-out / unevaluable patients. This design yields a type I error rate of 0.0466 and power of 0.8122 when the true response rate is 0.25. We believe that anything below a response rate of 25% would not be clinically meaningful given the potential risks of dabrafenib and trametinib. The likelihood of stopping early if the null hypothesis is true will be 0.63. A response rate of 25% or higher, in the context of other promising secondary endpoint results such as a high % of tumor necrosis, would warrant further study.

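### Does waiving response confirmation only for resected patients leave the 6-week primary endpoint undefined for everyone else?

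*Combined protocol and SAP*

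**What the plan says.** The objective in section 1.1 is "To observe the response rate of ameloblastoma to dabrafenib plus trametinib at 6 weeks". Section 10 repeats this as "Primary Outcome Measure: Response rate according to RECIST v1.1 at 6 weeks" and lists a 6-week time frame.

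Section 10.1 calls the criteria modified RECIST v1.1 and gives the reason: because some subjects are presurgical, "we will be unable to obtain response confirmation following the surgical resection of tumors". Section 10.1.1 then applies RECIST v1.1 "with the exception that for patients undergoing surgical resection there will be no confirmatory imaging as this would be irrelevant following surgical resection".

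Section 10.1.3 puts the initial evaluation for the primary endpoint at week 6 and adds: "For patients not undergoing surgical resection, follow-up imaging will be every 6 to 9 weeks", described as standard of care. Section 4.0 provides for unresected patients, who stay on treatment; their expected share is not given.

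Section 12.1 sets a Simon two-stage design with rates of 0.05 and 0.25. The trial stops if there is "less than one response (defined in Section 10.1) in these 9 patients", and at the end "The null hypothesis will be rejected if 3 or more responses are observed in 17 patients". The rates carry no confirmed or unconfirmed label beyond that pointer to Section 10.1.

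**The concern.** An exception written for one group normally means that the rule still binds the other. If confirmation is waived only after resection, an unresected patient's CR or PR would seem to need a second scan. The next scan comes 6 to 9 weeks after week 6, at about weeks 12 to 15, outside the stated time frame. The count in 12.1 would then pool unconfirmed week-6 responses (resected) with confirmed later ones (unresected), and the counted rate would depend on a surgical mix that the plan does not fix.

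The boundaries are small enough for this to matter. One response in 9 decides stage 1 and three in 17 decide the trial. Accrual also pauses at the ninth enrolment unless a response has been centrally documented, so the date on which a response counts could affect the pause. And if 5% and 25% meant something other than what is counted, the stated type I error and power would not describe the test.

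**Working it through.** **Step 1: the plan's own figures.** Inputs from 12.1: 9 patients in stage 1, 8 more in stage 2, continue with at least 1 response, reject with at least 3 of 17.

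P(reject) = sum over x ≥ 1 of P(X1 = x; 9, p) × P(X2 ≥ 3 − x; 8, p).

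- p = 0.05: 0.2985 × 0.0572 + 0.0629 × 0.3366 + 0.0084 × 1 = 0.0466 (stated 0.0466).
- p = 0.25: 0.2253 × 0.6329 + 0.3003 × 0.8999 + 0.3993 × 1 = 0.8122 (stated 0.8122).
- Early stopping under the null: 0.95^9 = 0.630 (stated 0.63).

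The arithmetic is right for any single definition of response shared by the rates and the count.

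**Step 2: which definition the text supports.**

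| Place | Points to |
|---|---|
| 1.1 objective | week 6 |
| 10 outcome and time frame | week 6 |
| 10.1 endpoint sentence | week 6 |
| 10.1.3 evaluation for the primary endpoint | week 6, though called initial |
| 10.1.3 later scans | follow-up and standard of care, not confirmation |
| 10.1.1 waiver | confirmation elsewhere, by implication only |

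No section says that an unresected response counts only after a second scan.

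**Step 3: what the literal reading would do.** Two inputs must be assumed: s, the share resected, and c, the share of week-6 responses that hold at the next scan. The counted rate is p × m, with m = s + (1 − s) × c, if 5% and 25% are unconfirmed week-6 rates. It is (p / c) × m if they are confirmed rates.

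For c, section 2.2 offers only melanoma figures: for dabrafenib alone, "Dabrafenib has been demonstrated to induce response rates of 52% with a duration median of 5.6 months", and for the combination a median PFS of 11.4 months. With exponential decay, c = 0.5^(t / median). The 5.6-month median (24.3 weeks) gives 0.843 at 6 weeks and 0.774 at 9 weeks; the 11.4-month median (49.6 weeks) gives 0.920 and 0.882. The range is about 0.77 to 0.92.

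With s = 0.5:

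| c | m | Rates unconfirmed: type I error, power | Rates confirmed: type I error, power |
|---|---|---|---|
| 0.77 | 0.885 | 0.034, 0.734 | 0.066, 0.886 |
| 0.92 | 0.960 | 0.042, 0.787 | 0.052, 0.837 |

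The two pairs are alternatives and cannot occur together.

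**Step 4: chance that the reading changes the verdict.** If responders under the literal rule are a subset of week-6 responders, this is the difference in rejection probability. At a true week-6 rate of 25%:

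- s = 0.5: 0.8122 − 0.7340 = 0.078 (c = 0.77); 0.8122 − 0.7872 = 0.025 (c = 0.92).
- s = 0.8: 0.8122 − 0.7833 = 0.029; 0.8122 − 0.8025 = 0.010.
- s = 1: zero.

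At a true rate of 5% and s = 0.5 it is 0.005 to 0.012.

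**Step 5: the confirmed-rate branch.** Its largest type I errors arise when every response is counted unconfirmed. With c = 0.75 and everyone resected, the counted null rate is 0.05 / 0.75 = 0.0667 and the type I error is 0.093. Counting all week-6 responses gives that same 0.093 for any surgical mix. This branch therefore depends on labelling 5% as a confirmed rate, which the plan does not do; settling how unresected patients are counted would not remove it.

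**The case for a change.** The best case for a change is textual. The protocol itself treats confirmation as the default that it modifies, and it limits the modification to resected patients. The word initial in 10.1.3 leaves room for a later determination, and the pointer from 12.1 leads back to the same text. In an open single-arm trial decided by one to three responses, an unsettled counting rule could in principle be chosen after the responses are known, and one sentence would close it.

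Part of this stands: the waiver's scope does carry an implication for unresected patients, and no section states the rule for them outright. The rest is weaker.

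- The rival reading rests on inference from an exception and would put the primary endpoint beyond the time frame given in three sections.
- In a one-sample test the true response rate is naturally the rate of whatever is counted. Two definitions appear only if they are supplied from outside the plan.
- The holding fraction comes from melanoma. One figure is for a single agent and the other is PFS rather than response duration. Section 2.1 describes ameloblastoma as benign and slow-growing, and neither figure captures measurement variation between scans.
- The subset assumption in the reversal probability fails if later scans could also add responders.

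**Conclusion.** No change to the plan follows. This is a gap in wording that analysts fill sensibly: CR or PR at the week-6 assessment, counted the same way for every patient at both the 9-patient and 17-patient looks. It is the only reading that applies to resected and unresected patients alike and agrees with sections 1.1, 10 and 10.1. On it, 5% and 25% are week-6 rates, and the sample size, boundaries, type I error 0.0466, power 0.8122 and early-stopping probability 0.63 stand as printed.

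The literal alternative would cost about 0.025 to 0.078 of power with half the patients resected and 77% to 92% of responses holding, less with more surgery, and nothing if every week-6 response holds. Neither the surgical share nor the holding fraction is in the documents, so these figures only bound what the unlikely reading might do. The conclusion rests on the week-6 time frame governing the count, which the weight of the text supports.

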10.1.2 Measurement Methods

Standard CT or MRI scans and physical exam, per RECIST v1.1 criteria, will be used to measure tumors for purposes of response assessment. To maintain consistency of data and quality of science, whatever imaging modality is used at baseline for each patient should be used throughout the trial.

10.1.3 Measurement Time Points

Initial response evaluation for the primary endpoint will be at 6 weeks. For patients not undergoing surgical resection, follow-up imaging will be every 6 to 9 weeks, which we consider to be standard of care.

10.2 Secondary Outcome

10.2.1 Tumor necrosis

One secondary outcome will be percent of tumor necrosis at the time of endpoint biopsy or surgical resection. We intend to use this outcome with criteria established for treatment response in other tumors.

10.2.2 Measurement Definition

The definition we will use for the first secondary endpoint of response will be evaluation of extent of tumor necrosis by H&E slide review. This will be performed on either the endpoint biopsy or the resection specimen.

10.2.3 Measurement Methods

Routine H&E slide review will be used to measure extent of tumor necrosis for purposes of response assessment. Percentage of tumor necrosis by volume will be assessed as routinely done with other solid tumors such as osteosarcoma. The biopsy slide or multiple slides of the resection specimen will be examined and the volume of the necrosis compared to the volume of the total tumor will be determined by the centrally reviewing pathologists and percentage readouts of tumor necrosis, in increments of 10%, will be determined. In addition to measuring tumor necrosis the slide review will also estimate therapy effect on intact cells by estimating the percent cells with therapy-associated nuclear atypia.

10.2.4 Measurement Time Points

Tumor necrosis evaluation for this secondary endpoint will be at the time of the endpoint biopsy or the surgical resection.

10.2.5 Response Review

Tumor necrosis evaluation will be centralized review by the study co-investigator, [name], and at least one designee with substantial experience with tumor necrosis evaluation. Disagreements concerning response assessment between the PI and the second reviewer will be adjudicated by a board certified pathologist with tumor necrosis evaluation experience.

10.3 Secondary Outcome – Proliferation index

A second secondary outcome will be proliferation index as measured by Ki67 percent positivity at the time of endpoint biopsy or surgical resection. We intend to use this outcome as measured with immunohistochemistry with criteria established for assessment of proliferation index for other tumors.

10.3.1 Measurement Definition

The definition we will use for the second secondary endpoint of response will be evaluation of percent proliferation index by Ki67 immunohistochemistry. This will be performed on the initial pre-treatment biopsy and either the endpoint biopsy or the resection specimen.

10.3.2 Measurement Methods

Proliferation index evaluation will be performed in the laboratory of [name] on the initial pre-treatment biopsy and either the endpoint biopsy or the resection specimen. Ki-67 immunohistochemistry will be scored by at least two pathologists using percentage positive cells as the primary metric. The results of the immunohistochemical analysis will be expressed as both raw data in addition to a ratio between pre- and post- treatment. All pathological evaluations will be done centrally by the pathology co- investigators, [name] and [name] or their designees.

10.3.3 Measurement Time Points

Proliferation index evaluation for this secondary endpoint will be at the time of the endpoint biopsy or the surgical resection.

10.3.4 Response Review

Proliferation index evaluation will be centralized review by the study co-investigator, [name] and [name] and at least one designee with substantial experience with proliferation index evaluation. Disagreements concerning response assessment between the PI and the second reviewer will be adjudicated by a board certified pathologist with proliferation index evaluation experience.

10.4 Secondary Outcome – Phosphorylation of MEK/ERK

A second secondary outcome will be expression of phosphorylation of MEK and ERK as measured by phospho-MEK/ERK positivity at the time of endpoint biopsy or surgical resection. We intend to use this outcome as measured with immunohistochemistry using antibodies specific for phospho-MEK/ERK and total MEK/ERK (either phosphorylated or

un-phosphorylated) with criteria established for assessment of protein expression by immunohistochemistry for other tumors.

10.4.1 Measurement Definition

The definition we will use for the second secondary endpoint of response will be evaluation of protein expression by immunohistochemistry. This will be performed on the initial pre-treatment biopsy and either the endpoint biopsy or the resection specimen.

10.4.2 Measurement Methods

Immunohistochemistry evaluation for MEK/ERK will be performed in the laboratory of [name] on the initial pre-treatment biopsy and either the endpoint biopsy or the resection specimen. Immunohistochemistry will be scored by at least two pathologists using percentage positive cells and intensity of staining as the primary metrics. The results of the immunohistochemical analysis will be expressed as both raw data in addition to a ratio between pre- and post- treatment. All pathological evaluations will be done centrally by the pathology co- investigators, [name] and [name] or their designees.

10.4.3 Measurement Time Points

Immunohistochemistry evaluation for MEK/ERK for this secondary endpoint will be at the time of the endpoint biopsy or the surgical resection.

10.4.4 Response Review

Immunohistochemistry evaluation for MEK/ERK will be centralized review by the study co-investigator, [name] and [name] and at least one designee with substantial experience with protein expression evaluation. Disagreements concerning response assessment between the PI and the second reviewer will be adjudicated by a board certified pathologist with protein expression evaluation experience.

11 REGULATORY CONSIDERATIONS

11.1 Institutional Review of Protocol

The protocol, the proposed informed consent and all forms of participant information related to the study (e.g. advertisements used to recruit participants) will be reviewed and approved by the Stanford IRB and Stanford Cancer Institute Scientific Review Committee (SRC). Any changes made to the protocol will be submitted as a modification and will be approved by the IRB prior to implementation. The Protocol Director will disseminate the protocol amendment information to all participating investigators. All participating sites will similarly have the informed consent document and protocol reviewed and approved by their local IRB and scientific review committee. There is to be only one version of the protocol to be used across all participating sites and no site can individually modify or amend the protocol at their site alone. That is, all protocol amendments and modifications must be reviewed and approved by all institutions' relevant review boards.

11.2 Data and Safety Monitoring Plan:

The Stanford Cancer Institute Data and Safety Monitoring Committee (DSMC) will be the monitoring entity for this study. The DSMC will audit study-related activities to determine whether the study has been conducted in accordance with the protocol, local standard operating procedures, FDA regulations, and Good Clinical Practice (GCP). This may

include review of the following types of documents participating in the study: regulatory binders, case report forms, eligibility checklists, and source documents. In addition, the DSMC will regularly review serious adverse events and protocol deviations associated with the research to ensure the protection of human subjects. Results of the DSMC audit will be communicated to the IRBs of all participating institutions and the appropriate regulatory authorities at the time of continuing review, or in an expedited fashion, as needed.

11.3 Data Management Plan

11.3.1 Data Collection

Data collection for this study will be via REDCap, a password protected HIPAA compliant web- based electronic data capture system. Prior to opening this study at any site, case report forms for the collection of all relevant required data will be developed and relevant site staff trained on the access and use of REDCap. Eligibility for each patient enrolled will be confirmed by the PI or designee centrally before authorization to enroll and patient number assignment is made via REDCap. The Protocol Director, or his/her designee, will prepare and maintain adequate and accurate participant case histories with observations and data pertinent to the study. At each participating site, that site's PI or designee is responsible for collecting and storing in one central location copies of all primary clinical documents and be prepared to transmit these documents via secure electronic means for remote audit and review. All sites should also be able to readily access actual primary documentation, either electronically or in paper form, for on-site audit purposes.

11.3.2 Data Submission responsibility

It is the responsibility of each site PI to ensure that all investigators and designees at that site understand and are trained in all the relevant procedures for data collection and submission. For the purposes of site data submission compliance, data will be considered delinquent and such delinquency reported to that site's IRB if the data for any required routine evaluation is not submitted within 4 weeks after the relevant visit, test, or assessment has been completed or resulted.

11.3.3 Multicenter Guidelines

The overall PI is responsible for distribution of all IND action letters and safety reports to all participating institutions.

12 STATISTICAL CONSIDERATIONS

12.1 Statistical Design and primary analysis

We propose a two stage Optimal design per Simon, *et al.* (Simon R, 1989. *Controlled Clinical Trials*. 10:1-10), and using the UNC calculator:

<http://www.csc.unc.edu/csc/aivanova/SimonsTwoStageDesign.aspx>

The null hypothesis that the true response rate is 0.05 will be tested against a one-sided alternative. In the first stage, 9 evaluable patients will be accrued. If there is less than one response (defined in Section 10.1) in these 9 patients, the study will be stopped. If at the time of the 9th patient's enrollment there has not been at least one centrally documented response, accrual will stop until responses have been centrally determined for the first nine patients. Otherwise, 8 additional evaluable patients will be accrued for a total of

17 evaluable patients. The null hypothesis will be rejected if 3 or more responses are observed in 17 patients. We will allow for up to 11 patients in the first stage and up to 10 patients in the second stage to account for patient drop-out / unevaluable patients. This design yields a type I error rate of 0.0466 and power of 0.8122 when the true response rate is 0.25. We believe that anything below a response rate of 25% would not be clinically meaningful given the potential risks of dabrafenib and trametinib. The likelihood of stopping early if the null hypothesis is true will be 0.63. A response rate of 25% or higher, in the context of other promising secondary endpoint results such as a high % of tumor necrosis, would warrant further study.

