12.2 Secondary Analysis

We will determine secondary responses for: 1) tumor necrosis; 2) proliferation index; and 3) ERK/MEK phosphorylation. These assays will be exploratory and not subjected to a prospective statistical plan for analysis. Tumor necrosis % will be estimated according the standard surgical pathology techniques. Proliferation index will be measured by percentage of cells in mitosis and Ki 67 staining per standard surgical pathology assays. The ratio of unphosphorylated to phosphorylated ERK and MEK will be done using standard phosphorylation specific antibodies on tumor tissue specimens in [name] lab according to his lab's SOPs. See Section 10 for details.

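### Does Section 12.1 leave the conclusion at 3 or 4 of 17 responses open by not saying whether its 25% is a true or an observed rate?

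*Combined protocol and SAP*

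**What the plan says.** Section 12.1 sets out a Simon optimal two-stage design. The hypothesis concerns a true rate: "The null hypothesis that the true response rate is 0.05 will be tested against a one-sided alternative". On the first stage it says "In the first stage, 9 evaluable patients will be accrued" and "If there is less than one response (defined in Section 10.1) in these 9 patients, the study will be stopped". Otherwise 8 more evaluable patients are added, making 17, and the final rule is "The null hypothesis will be rejected if 3 or more responses are observed in 17 patients". The operating characteristics follow: "This design yields a type I error rate of 0.0466 and power of 0.8122 when the true response rate is 0.25".

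The next sentence gives the clinical reasoning: "We believe that anything below a response rate of 25% would not be clinically meaningful", in view of the risks of the two drugs. The section closes with a remark about what would justify more research: "A response rate of 25% or higher, in the context of other promising secondary endpoint results such as a high % of tumor necrosis". Neither of these sentences says true or observed. On the tissue results named in the last one, Section 12.2 says: "These assays will be exploratory and not subjected to a prospective statistical plan for analysis".

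**The concern.** The section seems to hold two standards. The test succeeds at 3 of 17, an observed 17.6%, while the text says that rates under 25% are of no clinical interest.

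- **If 25% is an observed rate**, results of 3/17 and 4/17 reject the null yet fall short of the level for further study, which needs 5/17.
- **If 25% is a true rate**, rejection at 3/17 shows only that the rate exceeds 5%, and the plan does not spell that out.

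The tissue findings that accompany the 25% do not settle the matter, because they have no threshold and no planned analysis. What would be at stake is the reading of a borderline result. A rejection might be presented as having reached the meaningful level, with that interpretation chosen after the data are known.

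**Working it through.** **Inputs (all from Section 12.1).** First stage n1 = 9, stop at 0 responses; second stage n2 = 8; total n = 17; reject at 3 or more; null rate 0.05; alternative rate 0.25.

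**Step 1: the plan's own figures.** With X1 ~ Bin(9, p) and X2 ~ Bin(8, p),

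P(reject) = P(X1=1)·P(X2≥2) + P(X1=2)·P(X2≥1) + P(X1≥3).

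- At p = 0.05: 0.2985 × 0.0572 + 0.0629 × 0.3366 + 0.0084 = 0.0466.
- At p = 0.25: 0.2253 × 0.6329 + 0.3003 × 0.8999 + 0.3993 = 0.1426 + 0.2703 + 0.3993 = 0.8122.
- Early stopping under the null: 0.95^9 = 0.6302.

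All three match the plan. A search over designs with n up to 30, type I error at most 0.05 and power at least 0.80 also returns this design as Simon's optimal one.

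**Step 2: where the two standards could part.** 3/17 = 17.6%, 4/17 = 23.5%, 5/17 = 29.4%. Only counts of 3 and 4 reject the null with an observed rate under 25%.

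**Step 3: how often that happens.** P(3 or 4) = P(at least 3) − P(at least 5), each including survival of the first stage.

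| True rate | P(at least 3) | P(at least 5) | P(3 or 4) |
|---|---|---|---|
| 5% | 0.047 | 0.001 | 0.045 |
| 15% | 0.456 | 0.098 | 0.358 |
| 20% | 0.663 | 0.240 | 0.423 |
| 25% | 0.812 | 0.424 | 0.388 |
| 30% | 0.905 | 0.609 | 0.296 |
| 40% | 0.981 | 0.872 | 0.109 |
| 50% | 0.997 | 0.975 | 0.022 |

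At a true 25%, 0.388/0.812 = 48% of rejecting trials would end at 3 or 4. The zone shrinks quickly above the alternative.

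**Step 4: what 3 or 4 responses show.** The exact one-sided 95% lower bound, allowing for the two stages, is the p at which P(continue and total at least k) = 0.05. It is 5.1% for k = 3 and 8.5% for k = 4. Both exceed 5%, in line with the stated rejection. The two-sided 95% interval at 3/17 is 3.9% to 44.0%, so 25% is neither established nor excluded. The entries of 0.456 and 0.663 at true rates of 15% and 20% are the ordinary intermediate power of a test whose null is 5%.

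**Step 5: which reading the text supports.** The sentence on clinical relevance comes directly after the one giving power at a true rate of 0.25, using the same number. It reads as the reason for choosing that alternative. Read as an observed rate, it would contradict the rejection rule given a few sentences earlier.

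**The case for a change.** The strongest case for a change rests on the closing sentence of Section 12.1. It pairs 25% with something the trial will observe, the extent of necrosis, and says what would justify more research. That has the form of a go-forward criterion on observed data. On that reading the criterion needs 5/17, which has probability 0.424 at a true 25%, and the requirement for promising tissue results can only lower it. The affected outcomes are not rare: 3 or 4 responses has probability 0.39 at the plan's own alternative. A clarification would cost only a few words.

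Part of this stands. The two sentences do lack the qualifier, the pairing with necrosis gives some support to an observed reading, and no other section says how 3 or 4 responses bears on further research. Section 10.2 does describe central necrosis scoring in 10% steps, with criteria taken from other tumors, but it sets no threshold.

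The rest does not carry. The closing remark says what would support more work; it does not say that a lower result ends development, and it is not written as a decision rule. The power of 0.8122 is claimed for the test alone, so 0.424 contradicts nothing in the plan. That rejection supports only a rate above 5% is already what the stated null and one-sided alternative mean. Section 2.3 presents the trial as a pilot asking in a preliminary way for any sign of activity, and a prescribed verdict for each count is more than that purpose needs.

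**Conclusion.** No change is called for. This is a missing qualifier that an analyst would fill sensibly from the sentence before it. The design, cut-off and error rates are correct, and the primary conclusion at 3 or 4 of 17 is fixed in advance: a true rate of 5% is rejected, and nothing is claimed about 25%. Clarifying the wording would record what the hypotheses already imply and would change no result.

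What remains unstated is only how an observed 17.6% or 23.5% bears on a remark about later research. That situation arises with probability 0.39 at a true rate of 25%, 0.30 at 30% and 0.11 at 40%. These figures assume exactly 9 and then 17 evaluable patients, independent responses with a common rate, and the stopping rule applied as written. The judgement also rests on reading the first 25% sentence as the rationale for the alternative. If the sponsor did intend an observed 25% as a separate criterion, it would mean at least 5 of 17, reached with probability 0.42 at a true 25%, 0.61 at 30% and 0.87 at 40%. Even then the primary test would be unaffected.
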